10.2 Background Characteristics

10.2.1 Subject Disposition

The number of subjects in the following categories for the population will be provided:

- All Subjects Set
- Safety Set
- FAS
- Enrolled but never dosed

Number and percentage (based on the Safety Set) of subjects in each of the following categories will be provided:

- Completed study drug treatment
- Prematurely discontinued study drug treatment and the reason for discontinuation
- Completed study
- Prematurely discontinued the study and the reason for discontinuation

A listing will be provided for subjects who discontinued treatment or who discontinued study with reasons for discontinuation.

10.2.2 Demographics and Baseline Characteristics

Demographics and baseline characteristics will be summarized based on Safety Set.

Demographic data will include the following:

- Sex (male and female)
- Age at treatment initiation (months)
- Age group at treatment initiation
- Ethnicity (Hispanic or Latino; Not Hispanic or Latino; Not Collected per Local Regulations)
- Race (White; Black or African American; Asian; American Indian or Alaska Native;
 Native Hawaiian or Other Pacific Islander; Not Collected per Local Regulations; Other)

Baseline characteristics will include the following:

- Weight (kg)
- Length/height (cm)

- BMI (kg/m²)
- Weight-for-age z-score
- Length/height-for-age z-score
- BMI-for-age z-score
- Weight-for-length/height z-score
- Sweat chloride (mmol/L)
- FE-1 Levels (mg/kg)
- Serum IRT Levels (ug/L)
- Fecal Calprotectin Levels (mg/kg)

Medical history will be summarized based on Safety Set using the Medical Dictionary for Regulatory Activities (MedDRA) System Organ Class (SOC) and Preferred Term (PT). All demographic and baseline characteristic data will be listed.

10.2.3 Prior and Concomitant Medications

Medications used will be coded using the World Health Organization Drug Dictionary (WHODrug) and categorized as the following:

Prior medication: Any medication that started before the date of the first dose of study drug in Study 124.

Concomitant medication: Any medication continued or newly received during the TE Period.

Post-treatment medication: Any medication continued or newly received after the end of the TE Period.

A given medication can be classified as prior; concomitant; post-treatment; both prior and concomitant; both concomitant and post-treatment; prior, concomitant, and post-treatment.

Prior medications and concomitant medications will be summarized descriptively using frequency tables by preferred name and by ATC level 1 and 2 based on Safety Set.

All medications will be listed for each subject.

Details for imputing missing or partial start and/or stop dates of medication are described in Appendix.

10.2.4 Study Drug Exposure

Duration of study drug exposure is defined as follows: last dose date in the TE Period – first dose date in the TE Period + 1 day, regardless of any dose interruptions. If the last dose date of study drug is missing and the ETT visit is available, use the ETT visit as the last dose date. Otherwise, if there is no ETT visit, the last known study participation date will be used for analysis purposes.

Duration of study drug exposure as well as number of sticks administered, defined as (total number of sticks dispensed) – (total number of sticks returned), will be summarized descriptively based on the Safety Set for the TE Period. Additionally, the total duration of treatment exposure, defined as the sum of the subject's duration of treatment exposure and expressed in patient-years (1 patient-year is defined as one patient with 48 weeks of treatment), will be provided.

Study drug administration data will be presented in individual subject data listings.

Duration of exposure will also be summarized as a categorical variable (>0 to \leq 8 weeks; >8 to \leq 24 weeks; >24 to \leq 48 weeks; >48 to \leq 72 weeks; >72 to \leq 96 weeks; >96 weeks).

10.2.5 Study Drug Compliance

Study drug compliance will be calculated as follows: $100 \times (1 - [total number of days of study drug interruption in the TE Period] / [duration of study drug exposure]).$

The total number of days of study drug interruption is defined as the sum of the number of days of each study drug interruption in the TE Period, where the number of days of each study drug interruption is defined as the interruption end date – the corresponding interruption start date + 1.

Percent of stick packs taken will be calculated as follows: $100 \times (\text{total number of stick packs administered}) / (2 \times [\text{duration of study drug exposure in the TE Period}]).$

Treatment compliance percentages and percent of stick packs taken will be summarized descriptively based on the Safety Set. The number and percentage of subjects whose compliance is <80% or $\ge80\%$ and the number and percentage of subjects whose percent of stick packs taken is <80% or $\ge80\%$ will be summarized.

Study drug compliance and study drug interruption data will be presented in individual subject data listings in addition.

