### Follow-up Ophthalmological Examination

Subjects will have a Follow-up OE 24 weeks (± 14 days) after the last dose of study drug.

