### Discontinuation of Study Drug

If no convincing alternative etiology (e.g., acetaminophen use or viral hepatitis) for the elevated transaminases is identified, regardless of whether ALT or AST levels have improved, LUM/IVA treatment must be discontinued, after consulting with the Vertex medical monitor or authorized designee. Subjects in whom treatment is discontinued for elevated transaminases should have their transaminases monitored closely until levels normalize or return to baseline.

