9 ANALYSIS PERIOD

The analysis periods are described below.

The **Treatment-emergent (TE) Period** will start on or after the first dose date of study drug in Study 124 to 18 days (inclusive) after the last dose date of study drug in Study 124 or up to the last day in Study 124, whichever occurs first.

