Appendix E Blood Pressure Normal Levels for Boys and Girls by Age and Height Percentile

https://www.nhlbi.nih.gov/sites/default/files/media/docs/hbp_ped.pdf (pages: 10-13; accessed Oct 26, 2021)

Appendix F Programmable Important Protocol Deviation Programming Rules (Based on the Clinical Database)

Important Protocol Deviations during the Treatment Period:

- Compliance < 80% in Study 124
- Rollover Subject Study 122B completion
- LUM/IVA-naïve Subject age and inclusion/exclusion criteria

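### SAP compliance counts interruption days after the last dose but its denominator stops at the last dose, and the fallback for a missing last dose date has no cap

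*SAP*

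**What the plan says.** **Compliance.** SAP 10.2.5 takes 100 × (1 − ratio), where the ratio is "total number of days of study drug interruption in the TE Period] / [duration of study drug exposure". Each interruption is measured as "interruption end date – the corresponding interruption start date + 1". The denominator, from SAP 10.2.4, is "last dose date in the TE Period – first dose date in the TE Period + 1 day, regardless of any dose interruptions". SAP section 9 ends the TE Period at "18 days (inclusive) after the last dose date of study drug in Study 124", or at the last day in the study if that comes first. Compliance is tabulated at the 80% cut, and SAP Appendix F lists "Compliance < 80% in Study 124" among the programmable important protocol deviations (IPDs).

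**Interruption that becomes permanent.** Protocol 11.4.3 requires interruption at set liver-test thresholds, followed by a search for causes. If no convincing alternative cause is found, then "regardless of whether ALT or AST levels have improved, LUM/IVA treatment must be discontinued".

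**Missing last dose date.** SAP 10.2.4 first uses the ETT Visit. The next step reads: "Otherwise, if there is no ETT visit, the last known study participation date will be used for analysis purposes". The SAP does not define that date or limit it. Protocol 9.1.4 asks children who stop early to stay on study through Week 96, and Protocol 9.1.3 adds a later contact: "Subjects will have a Follow-up OE 24 weeks (± 14 days) after the last dose of study drug".

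**The concern.** The two parts of the compliance ratio cover different time. Days after the last dose can count as interruption but can never count as exposure. Nothing in the SAP cuts an interruption at the last dose, says how to close one that no dose follows, or keeps the result from going below zero. A child who took every dose until a stop that the protocol required could therefore be tabulated as non-compliant and meet the IPD rule.

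The exposure fallback has a related fault, because children remain on study without drug. A last participation date can fall well after the last dose. That would lengthen exposure, add patient-years and lower the percentage of stick packs taken. If the same date also sets the end of the TE Period, which the SAP does not say, off-drug events could be classed as treatment-emergent.

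**Working it through.** The plan gives no worked compliance or exposure value to reproduce, so its formulas are applied directly.

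**Inputs**
- TE Period: to 18 days after the last dose (SAP 9).
- Compliance cut: 80% (SAP 10.2.5, Appendix F).
- Week 96 target: day 96 × 7 + 1 = 673 (SAP Appendix A). The last dose is the one before that visit (Protocol 9.6), so about day 672 = 96 weeks.
- Safety Follow-up Visit: 14 ± 4 days after the last dose. Follow-up OE: 168 ± 14 days after it (Protocol 9.1.3).
- One patient-year (PY): 48 weeks = 336 days (SAP 10.2.4).

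**1. Compliance, no dose missed before the stop**

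Compliance = 100 × (1 − I/E). It is below 80% when I/E > 0.20, that is E < 5 × I, and below zero when E < I.

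With I = 18, the most that fits within the TE Period:
- E = 15: 100 × (1 − 18/15) = −20.0%
- E = 18: 0.0%
- E = 60: 70.0%
- E = 84: 78.6%
- E = 90: 80.0%
- E = 168: 89.3%
- E = 672: 97.3%

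The limits are E < 90 for the 80% cut and E < 18 for a negative value. With I = 5 they are E < 25 and E < 5.

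The range E < 90 can be reached. By target day, the scheduled on-treatment liver tests up to Week 12 (day 85) fall inside it: Day 15 and Week 12 for Rollover Subjects, and Day 15 and Weeks 4, 8 and 12 for LUM/IVA-naïve subjects.

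**2. Exposure of a completer, last dose on day 672, date missing, no ETT Visit**

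| Last participation read as | Excess days | Exposure (days) | Excess PY |
|---|---|---|---|
| Week 96 Visit | about 1 | 673 | 0.00 |
| Safety Follow-up Visit | 14 (10 to 18) | 686 (682 to 690) | 0.04 (0.03 to 0.05) |
| Follow-up OE | 168 (154 to 182) | 840 (826 to 854) | 0.50 (0.46 to 0.54) |

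On the last reading, the percentage of stick packs taken with full adherence falls to 100 × 672/840 = 80.0% (81.4% to 78.7%). The longer denominator can also hide real gaps: 150 interruption days give 77.7% over 672 days but 82.1% over 840.

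**3. Early stop without an ETT Visit, last participation at Week 96**

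A last dose on day 168 gives an excess of 673 − 168 = 505 days, about 72 weeks or 1.50 PY.

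**The case against.** The strongest reply is that the compliance effect depends on a data convention that the documents do not show. The formula needs an interruption with an end date. Protocol 13.1.1.6 separates a drug that is interrupted from one that is withdrawn, and Protocol 9.8 treats interruption as something dosing may resume from. If a permanent stop is entered only as a withdrawal, I = 0 and compliance is 100%. If the record stays open, SAP 10.1 bars imputation unless specified, so no 18 days arise, although the value is then undefined. A reader might infer that children stopped for toxicity will in general be shown as non-compliant. The documents do not support that: it depends on the convention, on the length of I and on an early stop.

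The IPD consequence is also softer than an automatic flag. SAP 10.2.6 has a review team identify IPDs under a plan. The stick-pack percentage, which does not use interruption days, would show such a child at about 100%. That cross-check does not help with the exposure fault, because it shares the exposure denominator.

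On exposure, a reader might infer that a missing date adds 24 weeks. That is only one reading of an undefined term. Protocol 12.3.2.1 equates completing the study with the Safety Follow-up Visit, which gives about 14 days. Missing dates are probably few: the ETT Visit is used first, a drug count is scheduled at Week 96, and Protocol 13.3 has missing data queried. If 50 children completed, total exposure would be about 50 × 672/336 = 100 PY, so one affected completer adds at most about 0.5%.

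These replies limit the size of the problem. They do not align the two windows or cap the fallback.

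**Conclusion.** Wrong as written, and minor. The windows in SAP 10.2.5 do not match, and the fallback in SAP 10.2.4 is uncapped and undefined.

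The compliance error needs a permanent stop kept as an interruption record with an end date. Even at 18 days it crosses the 80% cut only for exposure under 90 days, and a stop at day 168 still gives 89.3%. Protocol 12.3.2.4 has the same mismatch over a longer window, to the last day in Study 124, so the SAP narrows the fault without removing it.

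The exposure error needs a missing last dose date and no ETT Visit. For a completer it is about 1, 14 or 168 days, assuming the Week 96 Visit falls on its target day; it is larger for a child who stops early and is followed to Week 96. The number of such children cannot be found from the documents.

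The study is descriptive, so no test is affected. What can be wrong is the compliance table, the IPD count, the exposure and stick-pack summaries and, if the imputed date carries through, the TE Period and the rates per 100 PY.

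**What to change.** - **SAP 10.2.5:** count only interruption days between the first and last dose dates. An interruption never followed by a dose then contributes 0. A child with no missed dose before the stop scores 100% at any E, and no value can be negative.
- **SAP 10.2.4:** cap an imputed last dose date at the earliest of the ETT Visit, the Week 96 Visit and the recorded treatment discontinuation date, using whichever exist. A completer seen on the target day then has at most 673 days (2.00 PY).
- **Dispensing dates:** do not use one by itself as the last dose date. Later visits are 12 weeks apart, so this could understate exposure by up to about 84 days.
- **SAP 9:** state that the same date sets the end of the TE Period.

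The cost is minor SAP wording and programming. The change concerns analysis definitions only and alters no clinical rule.

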10.2.6 Important Protocol Deviations

A protocol deviation is any change, divergence, or departure from the study design or procedure defined in the protocol. An important protocol deviation (IPD) is a protocol deviation that may significantly impact the completeness, accuracy, and/or reliability of the study data or that may significantly affect a subject's rights, safety, or well-being.

IPDs will be identified by the Protocol Deviation Review Team according to the Protocol Deviation Plan.

The rules for identifying programmable IPDs based on the clinical database are defined in Appendix .

All IPDs will be summarized and presented in an individual subject data listing.

10.3 Efficacy Analysis

Not applicable.

10.4 Secondary Endpoint Analysis

10.4.1 Absolute Change from Baseline in Sweat Chloride

For each subject and at each time point, two sweat chloride measurements will be collected: one from the right arm and one from the left arm. Of the two measurements, only sweat chloride values obtained from sample volume $\geq 15~\mu L$ will be included in any analysis as a sample volume of at least 15 μL is required for testing. If a subject has replicated measurements at a postbaseline time point, then the median of the values will be used in data analyses. If the sweat chloride values for the left and right arms are both from sample volume $\geq 15~\mu L$, these values will be averaged together for the analysis; if only one arm is from sample volume $\geq 15~\mu L$, only that value will be used. Any sweat chloride values outside of the reportable range (i.e., < 10~mmol/L or > 160~mmol/L) will not be included in the analysis.

Raw values and absolute change from baseline in sweat chloride at each visit will be summarized descriptively (n, mean, SD, SE, median, minimum, and maximum) based on the FAS. In addition, the 95% confidence interval (CI) based on Normal approximation of the absolute change from baseline values will be provided. The mean (95% CI) of the absolute change from baseline at each scheduled time point will be plotted.

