# 9.1.4 Early Termination of Treatment OR Early Discontinuation

Subjects who prematurely discontinue LUM/IVA treatment will be asked to complete the ETT Visit as soon as possible after their last dose, to remain on study, and to complete the study assessments from the time of LUM/IVA treatment discontinuation through the Week 96 Visit and the Safety Follow-up Visit, if applicable. The assessments to be completed are shown in Table 3-1 and Table 3-2. If the ETT Visit occurs ≥10 days after the last dose of LUM/IVA, then a Safety Follow-up Visit will not be required. Additional safety assessments may also be performed at the discretion of the investigator, including possible consultation with a specialist consultant. The Vertex medical monitor will be informed about these additional assessments, and any additional data collected (e.g., as the result of an outside consultation) will be considered part of the study record to provide the most complete safety profile of the study drug.

Subjects who become eligible to receive commercially available LUM/IVA by prescription from a physician and who choose to continue onto commercially available LUM/IVA before completion of the study must remain on study-supplied LUM/IVA through the ETT Visit and may only initiate treatment with commercially available LUM/IVA after completion of this visit. Subjects who continue onto commercially available LUM/IVA will complete the Follow-up OE 24 weeks (± 14 days) after the last dose of study drug.

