# 10.7 Blinding and Unblinding

This is an open-label study.

However, the site and the subject's parent or legal guardian should not be informed of a subject's study-related sweat chloride (except if needed to confirm eligibility), IRT, FE-1, and markers of intestinal inflammation results during the study even if the subject permanently discontinued treatment.

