#### 12.3.1 General Considerations

All individual subject data will be presented in data listings based on the 124 All Subjects Set.

Continuous variables will be summarized using the following descriptive summary statistics: number of subjects, mean, SD, SE, median, minimum value (min), and maximum value (max).

Categorical variables will be summarized using counts and percentages.

**Baseline value** will be defined as the most recent non-missing measurement (scheduled or unscheduled) collected on or before the first dose of LUM/IVA in Study 124.

For sweat chloride, values at each visit will be based on averaged measurements from left and right arms as specified in Section 11.2.1. For Rollover Subjects, baseline will be defined as the most recent non-missing measurement (scheduled or unscheduled) collected on or before the first dose of LUM/IVA in Study 124. For LUM/IVA-naïve Subjects, baseline will be defined as the average of the values at screening and the pretreatment measurement on Day 1 of Study 124. If only 1 pre-first dose measurement of sweat chloride is available, that measurement will be considered the baseline.

Change (Absolute Change) from baseline will be calculated as postbaseline value – baseline value.

**Current Study Period** starts from the first dose of study drug in Study 124 to the last day in Study 124.

The Treatment-emergent (TE) Period for the Current Study Period starts on or after the first dose date of study drug in Study 124 to 14 days (inclusive) after the last dose of study drug in Study 124 or up to the last day in Study 124, whichever occurs first.

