#### 12.3.3 Secondary Endpoint Analysis

## 12.3.3.1 Absolute Change From Baseline in Sweat Chloride

Raw values and absolute change from baseline in sweat chloride at each visit of the Current Study Period will be summarized descriptively based on the 124 FAS overall. Descriptive statistics, including number of subjects, mean, SD, median, min, and max, along with the 95% CI based on Normal approximation, will be provided for the absolute change from baseline values. The mean (95% CI) of the absolute change from baseline values will be plotted.

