5.2 Secondary Objective

To evaluate the pharmacodynamics (PD) of long-term LUM/IVA treatment in subjects with CF, who are homozygous for *F508del* and 12 to <24 months of age at treatment initiation.

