10.6.2 Clinical Laboratory

For laboratory measurements, raw values and change from baseline values for the continuous hematology and chemistry results will be summarized in SI units at each visit of the TE Period.

Laboratory tests done in the local laboratory may be used in data analyses if data from the central laboratory are not available.

For hematology and chemistry, the number and percentage of subjects with abnormally low (< lower limit of normal [LLN]) values and with abnormally high (> upper limit of normal [ULN]) values at each visit will be summarized.

The number and percentage of subjects meeting the threshold analysis criterion during the TE Period of the TE Period will be summarized for selected laboratory parameters based on the Safety Set. The threshold analysis criteria are provided in Appendix.

In addition, listings containing individual subject hematology and chemistry values outside of the normal reference ranges will be provided. These listings will include data from both scheduled and unscheduled visits.

LFT elevations meeting ALT or AST > 5xULN, or ALT > 3xULN and total bilirubin > 2xULN, or AST > 3xULN and total bilirubin > 2xULN at one visit during the TE period will also be listed.

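### The by-visit sweat chloride table pools on-drug and post-discontinuation values without labelling them; an on-treatment table should sit beside it

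*SAP*

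**What the plan says.** **Objective.** SAP 5.2 gives the secondary objective as "To evaluate the pharmacodynamics (PD) of long-term LUM/IVA treatment in subjects with CF". Its only endpoint is the absolute change from baseline in sweat chloride (SAP 6.2).

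**Follow-up after stopping.** Protocol 9.1.4 asks children who stop early "to remain on study, and to complete the study assessments from the time of LUM/IVA treatment discontinuation through the Week 96 Visit". Protocol 10.7 withholds sweat chloride, IRT, FE-1 and inflammation-marker results from sites "even if the subject permanently discontinued treatment", so results from such children are foreseen.

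**PD summaries.** Protocol 12.3.3.1 has "Raw values and absolute change from baseline in sweat chloride at each visit of the Current Study Period will be summarized descriptively". Protocol 12.3.1 defines that period as one that "starts from the first dose of study drug in Study 124 to the last day in Study 124", whatever the date of the last dose. SAP 10.4.1 drops the named period: "Raw values and absolute change from baseline in sweat chloride at each visit will be summarized descriptively". SAP 10.5 is equally silent on period for growth, FE-1, IRT and fecal calprotectin. The analysis set is the FAS (SAP 8), and Appendix A counts study days from the first dose with no cut at the last dose.

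**Safety summaries.** SAP 10.6.2 says that laboratory results "will be summarized in SI units at each visit of the TE Period". SAP 10.6.3, 10.6.4 and 10.6.6 set the same limit for ECGs, vital signs and pulse oximetry.

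**The concern.** The secondary objective is about PD under long-term treatment. A child whose last dose was around Week 30 and who keeps attending supplies off-drug sweat chloride values at Weeks 48 and 96. These are averaged with values from children still taking the drug, and the table does not say how many contributors were off drug.

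With no comparator arm, the reader has only the by-visit mean and its interval. If the mean drifts back towards baseline at late visits, the table alone cannot separate loss of response on drug from a growing share of children off drug. The SAP limits its by-visit safety tables to the TE Period but says nothing for the PD tables, so a programmer must infer which values belong.

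**Working it through.** The plan has no figure to reproduce: it gives no sample size calculation, effect size, SD or discontinuation rate. The check traces example records through the rules, then shows how attenuation scales under stated assumptions.

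**1. Which values enter.** For rollover and naïve children alike, Appendix A maps sweat chloride to Week 48 for Days 254 to 505 (target 337) and to Week 96 for Days 506 to 680 (target 673). Take a last dose on Day 210:

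- Week 48 sample: 337 − 210 = 127 days after the last dose.
- Week 96 sample: 673 − 210 = 463 days after the last dose.

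Both enter their rows. Both lie past the end of the TE Period on either definition (Day 224 with 14 days, Day 228 with 18).

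**2. Which record is kept.** Take a last dose on Day 520, an ETT sample on Day 525 and a scheduled Week 96 sample on Day 673. Both samples fall in Days 506 to 680. For PD parameters, SAP 10.1 prefers the scheduled-visit record, then the one closest to target.

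- The Day 673 record is the scheduled Week 96 visit and is 0 days from target.
- The Day 525 record is 673 − 525 = 148 days from target.

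The Day 673 value is used on either criterion, 673 − 520 = 153 days after the last dose. The sample taken 5 days after the last dose is set aside. The rule in SAP 10.1 that moves an ETT visit to the follow-up visit does not apply, because it needs at least 10 days since the last dose.

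**3. Order of operations.** On either definition the TE Period (to Day 534 or Day 538) contains Day 525 and excludes Day 673. If the limit is applied first, Day 525 is retained. If the record is chosen first, Day 673 is selected and then removed, and the child has no on-treatment value in that row.

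**4. Possible size (illustration only).** Assume 50 contributors at a visit, a share q off drug and a fraction r of the on-drug change persisting off drug:

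observed mean ÷ on-drug mean = (1 − q) + q·r

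To compare the shift with the planned interval, let d be the on-drug change in SD units (assumed 1 to 2) and take r = 0:

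SD = √(1 + q(1 − q)d²); half-width = 1.96 × SD ÷ √50; shift = q·d

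For q = 0.10 and d = 1: SD = √1.09 = 1.044, half-width = 0.289, shift = 0.10, ratio = 0.35.

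| Off drug, of 50 | Attenuation, r = 0 | Attenuation, r = 0.5 | Shift ÷ 95% CI half-width, r = 0, d = 1 to 2 |
|---|---|---|---|
| 0 | 0% | 0% | 0 |
| 2 | 4% | 2% | 0.14 to 0.27 |
| 5 | 10% | 5% | 0.35 to 0.62 |
| 10 | 20% | 10% | 0.67 to 1.13 |

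A single on-drug change for everyone is a simplification. Naïve children have an untreated baseline, whereas the rollover baseline follows a 24-week treatment period in Study 122B.

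**The case against.** The strongest reply is that the protocol made a choice. Section 12.3.1 defines the Current Study Period and the TE Period side by side, and 12.3.3.1 selects the former for sweat chloride. With retention after stopping, that is a coherent treatment-policy summary. This stands. A reader might infer that the planned means are invalid or estimate nothing relevant to long-term treatment; the documents do not support that.

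Second, the contrast with the safety tables exists only in the SAP. The protocol summarises both kinds of data over the Current Study Period. The SAP defines only the TE Period and leaves the PD sections silent, and silence does not prove a deliberate difference. This also stands, but it is a reason to state the rule.

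Third, a reader might infer that the exploratory tables also fail the secondary objective. They have no objective of their own (SAP 5.3 lists none), so the argument from the objective rests on sweat chloride. Nothing in the documents shows that growth or FE-1 reverts when drug stops.

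Fourth, an on-treatment table is not cleaner in every respect. It also lacks a comparator, and its late rows describe only children who stayed on drug. The TE Period admits samples up to 14 or 18 days after the last dose and values during interruptions. That is why it should be added to the all-visits table and not replace it.

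Finally, the study is descriptive with safety as its primary objective, and the planned listings and disposition tables would let a reader trace off-drug values. That limits the importance of the point, but the by-visit tables themselves still show no such count.

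**Conclusion.** The point holds as a low-cost improvement. As written, the sweat chloride summary, and likewise the exploratory summaries, mix on-drug and post-discontinuation values without labels, and the record-selection rule can favour the off-drug value within a window. The all-visits mean is legitimate but does not by itself display the PD response on treatment.

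The size of any dilution cannot be known from the documents. It depends on how many children stop and still attend, and on how much effect persists. It is zero if none do, and 4% to 20% for 2 to 10 of 50 contributors off drug if no effect persists. These are assumed scenarios, so a claim of material dilution would go beyond the documents. It is also not stated whether children who move to commercial LUM/IVA contribute later visits; if they do, they are off study drug but still treated.

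**What to change.** In SAP 10.4.1:

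1. Keep the all-visits summary and label it as including values after discontinuation.
2. Add a by-visit on-treatment summary of sweat chloride. The same table for the 10.5 endpoints is optional.
3. Show the number of contributors off study drug at each visit.
4. Apply the on-treatment limit before choosing the record within a window.
5. Reconcile the TE Period, 14 days after the last dose in protocol 12.3.1 and 18 days in SAP 9, before using either as the limit.
6. State how values from children who moved to commercial LUM/IVA are handled.

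The cost is one extra set of descriptive tables built from dosing dates already held, with no new data collection. The on-treatment rows will have lower n at late visits and describe a selected group who stayed on drug, which a footnote should say.
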